# 9. Eligibility Criteria

### **Inclusion Criteria:**

- 1. All paediatric outpatients presenting to the study hospitals for medical treatment. The lower age limit will include children aged from 0 days, and the upper age limit will be in accordance to respective hospitals' practice for paediatric admissions (this may be 12, 15 or 19 years).
- 2. Informed parental/guardian consent provided.
- 3. Assent from children older than 13 years in addition to parental/guardian consent provided.

### **Exclusion Criteria:**

1. Patients presenting to the outpatient department for elective cases (e.g. elective surgery or change of dressing) or for clinical review appointment.

### 10. Intervention

This is a pre-post intervention study to develop and evaluate the effectiveness of a digital triage tool. Prior to the intervention period, hospital nurses will be trained and prepared for routine use of the digital triage tool. Patients who enroll in the study during the intervention period will be triaged by the hospital nurses who will be using the digital triage tool. The digital platform will consist of a mobile application hosted on an Android tablet integrating a pulse oximetry sensor attached to the tablet, with embedded smart algorithms that predict a critically ill state, or level of risk in a child presenting to the hospital. The platform will also include an interactive dashboard which will display the triage data to provide real-time monitoring for the clinicians who manage the patients. The dashboard will be implemented as a password protected website accessible by registered medical staff on any computer or tablet on the local network, allowing for easy and non-disruptive integration into health systems with existing electronic health records. ETAT+ criteria for triage will be incorporated as part of the digital platform (in addition to model identified from Phase I).

### 11. Outcomes

### **Primary Outcomes**

- 1. **Model Development:** Hospital admission (within 5 days of assessment) status determined from hospital records and information system, and a follow up call 7 days post discharge (to ascertain outcome). This will inform development of a clinical prediction model based on need for hospital admission.
- 2. Effectiveness Evaluation of Digital Triage Tool: Time to administration of an appropriate sepsis bundle of care, which includes at least one of antibiotics, intravenous

fluids, or oxygen as appropriate for age and clinical syndrome (treatment determined and administered by **hospital staff**). This will allow us to quantify the change from baseline in the proportion of children in each triage category (emergency, priority, queue) receiving treatment within 60 minutes of arrival at hospital.

### **Secondary Outcomes**

- 1. Length of hospitalization determined from hospital records, and a follow up call 7 days post-discharge.
- 2. Final diagnosis determined from hospital records.
- 3. 7-day post-discharge mortality status determined from a follow up call 7 days postdischarge.
- 4. 7-day readmission status determined from a follow up call 7 days post-discharge.
  - a. Facility of readmission.
  - b. Treatment received during readmission.

### 12. Participant Involvement

Total study participation time is estimated to be a maximum of 60 minutes per participant in both the baseline (Phase I) and intervention (Phase III) periods.

### Participant Involvement in Phase I and Phase III

Potential participants will be recruited by study nurses while they are waiting in line to be seen by the hospital triage nurses. Participants can anticipate study procedures (including consent, clinical examination, and interview) to take between 35 to 50 minutes. The **study nurses** will conduct study procedures in the triage waiting area, while the participant is waiting in line to be seen by the **hospital triage nurses**. If it is the participant's turn to be seen by the hospital triage nurses, study procedures will stop and there will be no interference or delays in accessing standard care. Participants will also engage in a short (10 minutes) follow up call 7-days postdischarge.

#### **Additional Procedures in Phase III**

In the intervention period, the **hospital triage nurses** will be conducting triage using the digital triage tool (which will include a digitized version of the triage guidelines in place at the study hospitals). Since our mobile health intervention will be integrated into standard care (**NOT** replacing standard care, but supplementing and strengthening existing triage systems), this will not require any additional time costs.

To reiterate, the **study nurses** will conduct the same study procedures (consent, clinical examination, and interview) in both the baseline (Phase I) and intervention (Phase III) periods. These procedures are conducted while the participants are waiting in line to be seen by the hospital triage nurses. The difference in Phase III is that the **hospital triage nurses** (that the participants are waiting in line to see) will be using the digital triage tool to triage participants.

### 13. Sample Size

### **Model Development Considerations**

The sample size for model development is based on a sampling strategy that takes into account the number of predictor variables (either binary or continuous) to be used in a model which has been used in a similar study [13]. This accounts for a minimum standard of 10 events per effective variable and can be expressed mathematically as:  $N = [n \times 10]/I$ , which demonstrates the relationship between the number of predictor variables (n), the event rate (I), and the required sample size (N). Our previous experience that allowed for a minimum of 10 events per selected variable (admission rate of 12% and 10 predictors) would estimate a sample of at least 833 children. The sample size needed to detect a 20% increase in the proportion of children who receive the bundle of care within one hour was calculated using the stats package in R.

### **Power to Detect Difference Considerations**

We have estimated the proportion of children who currently receive a bundle of care within one hour in the pre-intervention group to be 27%, based on findings from previous studies [19] and confirmed in our feasibility trial of the application and dashboard in Uganda. We will need at least 750 children for each of the pre-intervention and post-intervention conditions, using an alpha of .05, at power of 80%, to detect a 20% decrease in the proportion of children who receive the bundle of care within one hour.

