### Outcomes

#### Primary outcomes

**For model development** Hospital admission (within 5 days of assessment) status determined from hospital records, and a follow up call 7 days post discharge. This will inform development of a clinical prediction model based on need for hospital admission.

For effectiveness evaluation of digital triage tool An increase of at least 20% in the proportion of critically ill children (emergency and priority cases) receiving an appropriate bundle of care within 60 min of arrival at the hospital. An appropriate bundle of care is defined as at

least one of antibiotics, intravenous fluids, or oxygen as appropriate for age and clinical syndrome as determined and administered by **hospital staff**.

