## Sampling and recruitment Sample size

**Model development considerations** The sample size for model development is based on two components: the number of predictors expected in the final model (effect-ive variables), n, and the outcome event rate, I. We employ the typical minimum standard of 10 events per effective variable and calculate the sample size as  $N = (n \ x \ 10)/I$ . Based on our previous study at a Kenyan hospital [16], we estimate the admission rate as I = 12%, and thus, to allow for a model with 10 predictors we require a minimum sample of 833 children.

**Power to detect difference considerations** Based on an assumed pre-intervention rate of 27% of children who receive a bundle of care within 1 h, an assumed 20% relative increase due to the intervention, and an alpha of 0.05, an estimate of 750 children per group is needed for 80% power. The assumed pre-intervention rate is consistent with previous studies [19] and confirmed in our feasibility trial of the application and dashboard in Uganda.

**Selected sample size** Based on the uncertainty commonly present in these smaller sample sizes [20], the desire to include the possibly of modelling non-linearities in our models (using machine learning methods) and the clinical feasibility (large case load) we plan to target a larger sample of 4000 at each site, with a minimum sample size of 1000 participants enrolled in Phase I. Based on the activity at our selected sites this would require no more than a 60% recruitment rate during a sixmonth period.

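### 750 children per condition gives about 63% power (two-sided), not 80%, for a 20% relative increase from 27%, and the protocol states the effect in the wrong direction

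*Combined protocol and SAP*

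**What the plan says.** Protocol v5.0, Section 13, Power to Detect Difference Considerations, takes 27% as the proportion of children now receiving the bundle within one hour. It asks for "at least 750 children for each of the pre-intervention and post-intervention conditions, using an alpha of .05, at power of 80" percent. The purpose it gives for that number is "to detect a 20% decrease in the proportion of children who receive the bundle of care within one hour". The preceding subsection, Model Development Considerations, gives the opposite direction: "The sample size needed to detect a 20% increase in the proportion of children who receive the bundle of care within one hour". It attributes the calculation to R's stats package.

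The published protocol article (Sampling and recruitment, Sample size) uses the same 27% and alpha 0.05 with "an assumed 20% relative increase due to the intervention", and concludes that "an estimate of 750 children per group is needed for 80% power". It is the only place that calls the 20% relative. Neither calculation says whether the test is one- or two-sided.

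The children counted also differ. The article's primary effectiveness outcome, assessed at 60 minutes, is "An increase of at least 20% in the proportion of critically ill children (emergency and priority cases) receiving an appropriate bundle of care". Section 11 of Protocol v5.0 refers to the "proportion of children in each triage category (emergency, priority, queue) receiving treatment within 60 minutes of arrival at hospital". The 750 is given for children without restriction.

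Under Selected Sample size, both documents then set a target of 4000 at each site with a minimum of 1000 enrolled in Phase I. The reasons given are uncertainty at smaller sample sizes, modelling of non-linearities and feasibility.

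**The concern.** This is the only written power justification for the effectiveness comparison. If 750 per condition does not deliver 80% power for the stated effect, the plan overstates its chance of detecting that effect at the only size it names for the post-intervention period. Read literally, the protocol is also powered to detect the tool making timely treatment less common, which is contrary to the study's aim and to its own preceding subsection.

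The gap matters most if enrolment falls short of the 4000 target, or if only emergency and priority cases enter the primary comparison. In either case the reader has no valid power figure to fall back on. Shortfall is a real possibility: Section 8 of Protocol v5.0 reports that Phase I could not be started in Nairobi.

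**Working it through.** **Inputs.** Baseline p1 = 0.27, alpha = 0.05, power = 80% and n = 750 per condition (both documents). Effect: 20% relative increase (article), so p2 = 0.27 × 1.20 = 0.324. No dropout allowance is stated, and none is applied. Sidedness is not stated, so both are shown.

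**Sample size.** With equal groups and pbar = (p1 + p2)/2:

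n = [z_α √(2 pbar(1 − pbar)) + z_β √(p1(1 − p1) + p2(1 − p2))]² / (p2 − p1)²

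- For 0.27 against 0.324: pbar = 0.297, 2 pbar(1 − pbar) = 0.41758, p1(1 − p1) + p2(1 − p2) = 0.1971 + 0.21902 = 0.41612.
- Two-sided: (1.960 × 0.64621 + 0.8416 × 0.64508)² / 0.054² = (1.2665 + 0.5429)² / 0.002916 = 1,122.8, so **1,123 per condition**.
- One-sided: (1.0629 + 0.5429)² / 0.002916 = 884.3, so **885 per condition**.

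**Power at 750.** The standard error under the null is √(0.41758/750) = 0.02360, and under the alternative √(0.41612/750) = 0.02355.

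- Two-sided: Φ[(0.054 − 1.960 × 0.02360)/0.02355] = Φ(0.329) = **62.9%**.
- One-sided: Φ[(0.054 − 1.645 × 0.02360)/0.02355] = Φ(0.645) = **74.0%**.

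R's `power.prop.test`, from the package the protocol cites (the function itself is not named there), gives the same values. A simulation of 400,000 replicates gave 63.0% and 74.0%. Unpooled-variance and arcsine versions move n by one or two. A continuity correction raises it to 1,160 (two-sided) or 921 (one-sided).

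**Other readings of the 20%.**

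| Reading | n needed, two-sided | Power at 750, two-sided | n needed, one-sided | Power at 750, one-sided |
|---|---|---|---|---|
| 27% to 32.4% (relative increase) | 1,123 | 62.9% | 885 | 74.0% |
| 27% to 21.6% (relative decrease) | 990 | 68.4% | 779 | 78.7% |
| 27% to 47% (absolute increase) | 91 | over 99% | 72 | over 99% |
| 27% to 7% (absolute decrease) | 55 | over 99% | 43 | over 99% |

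None gives 750. The closest is the one-sided relative decrease, which needs an unstated one-sided test and the direction contradicted elsewhere. With 750 per condition and 80% two-sided power, the smallest detectable increase is from 27% to about 33.6% (24.6% relative).

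**Power at larger numbers** (27% to 32.4%, two-sided, all enrolled children): 1,000 per condition gives 75%. An even split of 4000 at one site, 2,000 per phase (my assumption), gives 96%.

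**Scenarios only.** These rest on assumptions the documents do not settle.

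- *Smaller Phase III.* Suppose Phase I enrols 1,250 per experimental site (1000 plus the 250 added for COVID-19) and Phase III enrols 750 in total. Power is 81.5% with two sites pooled (2,500 against 750) and 73% with one site alone (1,250 against 750).
- *Only emergency and priority cases count.* Their share is not given. With 2,000 enrolled per phase and the same 27% and 32.4% in that subset, 80% power needs a share of about 1,123/2,000 = 56%. Power is 46% at a 25% share, 75% at 50% and 90% at 75%.
- *Difference-in-differences*, the article's primary analysis. With four equal independent cells and no change at the control, SE = √[(3 × 0.27 × 0.73 + 0.324 × 0.676)/n]. Power is about 38% at 750 per cell and 77% at 2,000 per cell.

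**The case against.** The strongest answer is that 750 is a floor and the selected size is much larger. If 4000 is the total at a site, even an uneven split is adequate for the simple comparison: 1,000 against 3,000 gives about 90%, and 1,250 against 2,750 about 93%. That stands, and it makes this a correction to the justification rather than to the study's size. It does not make the statement right. The stated minimum covers Phase I only, and the target is not split between phases.

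Second, Protocol v5.0 does not itself say the 20% is relative. On an absolute reading, 750 is far more than needed. That is a fair caution about scale, but the absolute reading does not produce 750 either, and the article, with the same inputs and the same 750, says relative.

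Third, 750 is roughly right if 27% is taken as 20% below 33.75%: two-sided n = 728, with 81% power at 750. This might explain both the figure and the word *decrease*. It is conjecture, and it describes a 25% relative increase (33.75/27 = 1.25), so the text would still need correcting.

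Finally, the triage-category and difference-in-differences scenarios raise separate questions about the outcome population and the choice of primary analysis. Section 17 of Protocol v5.0 lists other methods. The arithmetic point does not depend on them.

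**Conclusion.** The concern holds. For the effect the article states (27% to 32.4%, alpha 0.05, two equal independent groups, all enrolled children), 750 per condition gives about 63% power two-sided or 74% one-sided, against the stated 80%. The shortfall is 17 or 6 percentage points. About 1,123 (two-sided) or 885 (one-sided) per condition would be needed. Under the literal decrease, the shortfall is 12 points two-sided and 1 point one-sided. The contradiction in direction is plain from the text and needs no calculation.

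The practical effect on the simple comparison is small if the 4000-per-site target is met. It is not small if enrolment falls towards 750 in the post-intervention condition, or if the primary comparison uses a subset or a design that needs more children. This should be fixed before the plan is relied on.

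**What to change.** In Section 13 of Protocol v5.0, under Power to Detect Difference Considerations:

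1. Change *decrease* to *increase*, to agree with the preceding subsection and the article.
2. State the scale (relative, as in the article, if the sponsor confirms it for v5.0) and whether the test is one- or two-sided.
3. Either replace 750 with about 1,123 per condition, or keep 750 and state about 63% power (both two-sided). Rerun the R call and quote its inputs.
4. Restate power for the comparison that will be primary, at the planned Phase I and Phase III numbers. Say whether those numbers are per site or per condition, and whether only emergency and priority cases count.

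The published article cannot be amended through the protocol; a note in the protocol or SAP that its power statement is superseded would do. The cost is wording and one rerun calculation. Eligibility, analysis and target enrolment do not change.

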#### Selected Sample size

Based on the uncertainty commonly present in these smaller sample sizes [20], the desire to include the possibly of modelling non-linearities in our models (using machine learning methods) and the clinical feasibility (large case load) we plan to target a larger sample of 4000 at each site, with a minimum sample size of 1000 participants enrolled in Phase I. Based on the activity at our selected sites this would require no more than a 60% recruitment rate during a sixmonth period.

### Changes due to the impact of COVID-19:

We hypothesize that the case mix of the "pandemic period" cohort is likely to be different to the case mix seen during "non-pandemic" times. This includes a potential increase in the average severity of disease in those children presenting at the facility. We are requesting support for the addition of a pandemic phase in Phase 1 – the baseline observational component of PRST. This will include a 25% increase in sample size at each experimental site (250 additional participants per experimental site). This increase in sample size is critical to developing a risk stratification model that is robust during pandemic and non-pandemic times.

# 14. Sampling and Recruitment Strategies

A systematic method for enrollment based on order of arrival at pre-selected time cut-offs will be adopted to avoid bias in participant selection by the study nurses. Patient arriving at the

outpatient are given a number upon registration (unless they are emergency cases that require resuscitation) and this number will be used to systematically sample patients during periods of busy workload.

A timekeeper will the record arrival time and sampling number for each patient in a notebook. When it is time to select a participant, the study nurse will report to the timekeeper, who will provide the sampling number of the first participant to arrive after the pre-selected time cut off. The study nurse will then approach and screen this patient. If the patient does not consent, the study nurse will move on to the second participant to arrive after the pre-selected time cut off, and so on.

The interval between time cut-offs will correspond to the estimated time taken for a study nurse to consent and collect data from a participant (35-50 minutes) to maximize productivity. When there is more than one study nurse on a given shift, the time intervals will be staggered.

# Methods: Data Collection, Management, and Analysis

# 15. Data Collection

### Predictors, Hospital Outcomes, 7-day Follow-up Calls

All study nurses will be trained and well versed on the standard operating procedures to facilitate standardization of all measurements. Study nurses will collect data using a custom-built Android application on a Samsung Galaxy Tablet A8. The list of predictors to be collected include clinical signs and symptoms, demographic/sociodemographic data, and pregnancy/birth information (see Appendix A). Similarly, designated study nurses will obtain hospital outcomes (see Appendix A) from patient records and enter them into the application on the Samsung Galaxy Tablet. Study nurses will conduct 7-day follow up calls in accordance with the standard operating procedures and enter the data into the application on the Samsung Galaxy Tablet.

### **Time Outcomes**

Timing tracking will be automated using customised RFID. RFID uses radio-frequency electromagnetic fields to identify the location of patients carrying special tags, with the help of readers located in key locations around the hospital, including the registration area, triage examination rooms, and treatment rooms. We intend to use Low Energy Bluetooth (BLE) tags that have a diameter of approximately 3cm and weigh <20g (see Figure 1). These tags will be inserted into a custom, washable arm, wrist or leg band. The tag could also be retained by the caregiver if the child was not willing to have the tag attached to them. When in close vicinity to a reader (for example, in the same room), the tag (location beacon) sends a message to a strategically located receiver to track the time at which the patient was in that precise location. Initially, manual tracking will also be conducted by designated study staff who will be situated in the same key locations as the RFID readers in order to validate the RFID system and ensure optimal performance.

Figure 1: Picture of RFID patient tracking tag

### **Usability Testing Data**

Think Aloud transcriptions and observer checklists will be entered into a computer and uploaded to REDCap. The Triage Tool Training Questionnaire (Appendix D) will be captured on paper and stored in a locked cabinet, in a locked room in our research spaces nearby the study sites.

#### **Hospital Staff Interviews**

Throughout Phase III of the study, healthcare workers and hospital staff will be invited to participate in an interview to allow for evaluation of the acceptability, usability, and feasibility of the digital triage tool in the context of the hospital. (Appendix E). This will be used to generate a report that provides insight on the overall perception of health worker's experiences with the digital triage tool and make updates as necessary.

### 16. Data Management

#### **Data Collection Infrastructure**

Study Nurses will collect data using a custom-built Android application, created using LambdaNative (lambdanative.org), the open-source cross-platform toolkit developed internally at BC Children's Hospital Research institute. All data entered into the mobile application is stored in an encrypted database using the encryption cipher Rabbit. Access to the tablet and application is secured by passwords; without using the application, the encrypted files are not readable. The Masimo iSpO2® Pulse Oximeter with Micro USB Connector will be used to collect pulse oximetry and heart rate (including 30 seconds of raw plethysmographic data) and the Masimo CaregiverTM non-contact thermometer will be used to measure core temperature. The data collection application also contains complex error checking specific to the survey questions such as date inconsistency checks and ensures only relevant data items are collected, by dynamically hiding redundant questions.

Due to the complex nature of a large multi-center study, data will be uploaded directly from the Android tablets to REDCap (Research Electronic Data Capture, https://projectredcap.org/). REDCap is a secure web-based application designed to support data capture for research studies and it has been used for over 300,000 projects, in over 100 countries, including prior studies in Uganda [17]. Encrypted data will be stored for less than 14 days after completion of data collection on the tablets. In Kenya, the data will be directly uploaded weekly (depending on internet availability) over a secured internet connection to KTWRP servers, where it will be stored. A deidentified copy will be sent to the central study server at the BC Children's Hospital Research institute where data will be checked for completeness and consistency with data definitions. In Uganda, the data will be sent to the central study server at the BC Children's

Hospital Research Institute. After this upload, the data on the tablets will be deleted. Each subject will be given a unique number and all data will be connected to this unique number. Using REDCap limits the amount of paper-based data, further ensuring data integrity and safety. The uploaded data will be accessible to only study team members with secure access to the server.

Data collected during follow-up interviews conducted by phone or in person will also be collected electronically and shared in the same secured manner. Personal identifiers are required for the collection of admission data and follow-up data. The data collection application contains several forms. All identifiers are collected on a single form, separate from the other forms containing non-identifying information, and stored in a separate and restricted REDCap form. Access to identifiers will be limited to those requiring this data for follow-up (i.e. only study personnel involved in follow-up or data verification). No analysts, co-investigators or principal investigators not directly involved in the follow-up or data verification will have access to this data. Access to REDCap will require 2-way authentication: in addition to the normal password process, a secure code (sent via SMS to the user) will be required for access to this data.

Paper based data collection items include consent forms and research assistant field notes (which do not contain identifiers). These will be stored in a locked cabinet, in a locked at our research spaces next to each study site.

